10.1 Regulatory and ethical compliance

This clinical study was designed and shall be implemented and reported in accordance with the ICH Harmonized Tripartite Guidelines for Good Clinical Practice, with applicable local regulations (including European Directive 2001/20/EC, US 21 CFR, and Japanese Ministry of

Health, Labor, and Welfare), and with the ethical principles laid down in the Declaration of Helsinki.

10.2 Informed consent procedures

Eligible subjects may only be included in the study after providing written (witnessed, where required by law or regulation), IRB/IEC-approved informed consent, or, if incapable of doing so, after such consent has been provided by a legally acceptable representative(s) of the subject. In cases where the subject's representative gives consent, the subject should be informed about the study to the extent possible given his/her understanding. If the subject is capable of doing so, he/she should indicate assent by personally signing and dating the written informed consent document or a separate assent form. Informed consent must be obtained before conducting any study-specific procedures (i.e., all of the procedures described in the protocol). The process of obtaining informed consent should be documented in the subject source documents.

Novartis will provide to Investigators in a separate document a proposed informed consent form that complies with the ICH GCP guideline and regulatory requirements and is considered appropriate for this study. Any changes to the proposed consent form suggested by the Investigator must be agreed to by Novartis before submission to the IRB/IEC, and a copy of the approved version must be provided to the Novartis monitor after IRB/IEC approval.

Women of child bearing potential should be informed that taking the study treatment may involve unknown risks to the fetus if pregnancy were to occur during the study and agree that in order to participate in the study they must adhere to the contraception requirement for the duration of the study. If there is any question that the subject will not reliably comply, they should not be entered in the study.

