Study treatment	All investigational drug(s) whose properties are being tested in the study as well as their associated treatment controls. This includes any placebos, any active controls, as well as approved drugs used outside of their indication/approved dosage or tested in a fixed combination. Investigational treatment generally does not include protocol-specified concomitant background therapies when these are standard treatments in that indication
Study treatment discontinuation	Point/time when patient permanently stops taking study treatment for any reason; may or may not also be the point/time of premature patient withdrawal
Subject Number	A number assigned to each patient who enrolls into the study
Variable	A measured value or assessed response that is determined in specific assessments and used in data analysis to evaluate the drug being tested in the study

Amendment 3

Rationale for amendment

The purpose of Amendment 3 is to revise the list of cardiometabolic biomarkers under investigation in this study. The following sections have been updated to reflect the correct cardiometabolic biomarkers:

- [Protocol Summary](#)
- [Section 2.2](#)
- [Section 6.4](#)
- [Section 6.4.2](#)

Changes to specific sections of the protocol are shown in the track changes version of the protocol using strike through red font for deletions and red underlined font for insertions.

A copy of this amended protocol will be sent to the Institutional Review Board (IRBs)/Independent Ethics Committees (IECs) and Health Authorities as required.

Protocol summary

Protocol number	CAIN457AUS02
Title	A randomized, double-blind, placebo-controlled, parallel-group, multicenter study to evaluate the effect of secukinumab on aortic vascular inflammation and cardiometabolic biomarkers after 12 weeks of treatment, compared to placebo, and up to 52 weeks of treatment with secukinumab in adult subjects with moderate to severe chronic plaque-type psoriasis
Brief title	Study to evaluate the effect of secukinumab compared to placebo on aortic vascular inflammation in subjects with moderate to severe plaque psoriasis
Sponsor and Clinical Phase	Novartis / Phase IV
Investigation type	Drug
Study type	Interventional

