3.1.4 Open-label treatment period (Week 16 through Week 52)

[figure not shown]
All subjects who complete the Double-blind Induction Period will enter the Open-label Treatment Period. The Open-label Treatment Period is defined as Week 16 through Week 52. All subjects in

the Open-label Treatment Period will receive secukinumab 300 mg s.c. at four-week intervals beginning at Week 16 through Week 48 (last dose during the Open-Label Treatment Period).

Self-administration of the doses at Weeks 16, 24, 32, 40, and 48 will take place at the study site; the doses at Weeks 20, 28, 36, and 44 will be self-administered at home.

All subjects who discontinue study treatment prematurely for any reason before the end of the Open-label Treatment Period should return to the study site for the performance of the Visit 14/Week 52 End of Treatment 2 (EOT2) assessments. The EOT2 visit should be scheduled 28 days (± 7 days) after the last dose of study treatment.

Figure 3-1 Study design

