4.2 Exclusion criteria

Subjects fulfilling any of the following criteria are not eligible for inclusion in this study. No additional exclusions may be applied by the Investigator, in order to ensure that the study population will be representative of all eligible subjects.

1. Forms of diagnosed psoriasis other than chronic plaque psoriasis (e.g., erythrodermic, generalized or localized pustular psoriasis, or new onset guttate psoriasis)
2. Medication-induced or medication exacerbated psoriasis (e.g., new onset or current exacerbation from beta-blockers, calcium channel inhibitors or lithium)
3. Previous exposure to secukinumab or any other biologic drug directly targeting IL-17A or IL-17RA receptors (e.g., ixekizumab, or brodalumab)
4. Diagnosis of other active ongoing skin diseases or skin infections (bacterial, fungal, or viral), or inflammatory diseases other than psoriasis that may interfere with the evaluation of psoriasis
5. Subjects not willing to limit UV light exposure (e.g., sunbathing and/or use of tanning devices) during the course of the study

6. Ongoing use of prohibited psoriasis treatments (e.g., topical or systemic corticosteroids, other topical medications, systemic psoriasis treatments oral or biological, UV therapy); washout periods detailed in the protocol must be followed (Table 5-2)
7. Use of any investigational drug within 4 weeks prior to Randomization, or within a period of 5 half-lives of the investigational treatment prior to Randomization, whichever is longer
8. Subjects using cholesterol-lowering medication (e.g., statins) and not on a stable dose for at least 90 days prior to randomization and unable to remain on a stable dose for the duration of the study
9. Pregnant or nursing (lactating) women, where pregnancy is defined as the state of a female after conception and until the termination of gestation, confirmed by a positive human chorionic gonadotropin (hCG) laboratory test
10. Women of child-bearing potential, defined as all women physiologically capable of becoming pregnant, unless they are using effective methods of contraception during dosing of study treatment and for 16 weeks after stopping treatment. Effective contraception methods include:
 - Total abstinence (when this is in line with the preferred and usual lifestyle of the subject. Periodic abstinence (e.g., calendar, ovulation, symptothermal, post-ovulation methods) and withdrawal are not acceptable methods of contraception

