5.5.9 Discontinuation of study treatment

Subjects may voluntarily discontinue study treatment for any reason at any time. They may be considered withdrawn if they state an intention to withdraw, fail to return for visits, or become lost to follow-up for any other reason. Subjects who prematurely withdraw from the study will not be replaced.

If discontinuation occurs for any reason during the study, the Investigator/qualified site staff must make every effort to determine the primary reason for a subject’s discontinuation from the study. This information will then be recorded on the End of Treatment eCRF for either the Double-blind Treatment Period (Visit 8/Week 12 EOT1), or the Double-blind Induction and Open-label Treatment Periods (Visit 14/Week 52 EOT2) as appropriate.

Study treatment must be discontinued and the subject withdrawn from the study if the Investigator on balance believes that continuation would be detrimental to the subject’s well-being. Study treatment **must** be discontinued under the following circumstances:

- Emergence of the following AEs: AEs that in the judgment of the Investigator/qualified site staff, taking into account the subject’s overall status, prevent the subject from continuing study treatment (for example, sepsis or serious infection);
- Any laboratory abnormalities that in the judgment of the Investigator/qualified site staff, taking into consideration the subject’s overall status, prevents the subject from continuing study treatment;
- Pregnancy (see [Section 6.5.6](#) and [Section 7.3](#));
- Ongoing use of any prohibited treatment, use of a prohibited treatment that results in an undue safety risk for the subject as per the Investigator’s clinical judgment, or receipt of a live virus vaccine during the study (as detailed in [Section 5.5.8](#));
- Emergency unblinding;
- Any other protocol deviation that results in a significant risk to the subject’s safety or significantly affects the validity of the study assessments.

Subjects who discontinue study treatment should undergo an end of study visit and then be discontinued from the trial.

- **Double-blind Treatment Period:** For subjects who discontinue study treatment prematurely before the end of the Double-blind Treatment Period, the Visit 8/Week 12 EOT1 assessments should be performed. **NOTE: Consultation with the Medical Monitor is required to**

determine if the FDG-PET/CT scan assessment should be performed during the discontinuation visit.

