5.5.13 Study completion and post-study treatment

A subject's individual study participation is completed once Visit 14/Week 52 of Open-label Treatment has been completed. After this date, any SAEs that occur in the following 30 days must be reported. The Investigator will also follow any AEs for which there is no outcome that can be reported at the final study visit.

The study as a whole will be completed once all randomized subjects have completed the study as per the protocol and the clinical database has been locked. Recruitment into the study will be terminated by the sponsor once the targeted number of randomized subjects has been met or is foreseen to be met with the subjects already in screening. Subjects who have been screened and have a screening visit recorded in the IRT system at the time that the planned enrollment number is met will be allowed to enter the trial and to be randomized if they are eligible.

Upon completion of their study participation, subjects will return to individual treatment, as determined by their treating physician.

The Investigator must provide follow-up medical care for all subjects who are prematurely withdrawn from the study, or must refer them for appropriate ongoing care.

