7.3 Pregnancy reporting

To ensure subject safety, each pregnancy occurring while the subject is on study treatment must be reported to Novartis within 24 hours of learning of its occurrence. The pregnancy should be followed up to determine outcome, including spontaneous or voluntary termination, details of the birth, and the presence or absence of any birth defects, congenital abnormalities, or maternal and/or newborn complications.

Pregnancy should be recorded on the Clinical Trial Pregnancy Form and be reported by the Investigator/qualified site staff to the local Novartis Drug Safety and Epidemiology Department. Pregnancy follow-up should be recorded on the same form and should include an assessment of the possible relationship to the study treatment.

Any SAE experienced during the pregnancy must be reported on the SAE Report Form.

8 Data review and database management

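### Contraception is required for 16 weeks after the last dose, but the consent text (10.2) and the pregnancy-reporting rule (7.3) do not cover that period

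*Protocol*

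**What the plan says.** Exclusion criterion 10 (Protocol 4.2) bars women of child-bearing potential unless they are "using effective methods of contraception during dosing of study treatment and for 16 weeks after stopping treatment".

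Protocol 10.2 says what these women are to be told and to agree to. On the agreement, "they must adhere to the contraception requirement for the duration of the study". On the risk, they are to be informed that "taking the study treatment may involve unknown risks to the fetus if pregnancy were to occur during the study".

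Protocol 7.3 sets the reporting rule: "each pregnancy occurring while the subject is on study treatment must be reported". A reported pregnancy is then followed to its outcome.

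The end of participation is fixed elsewhere. Under 5.5.13, a subject's "individual study participation is completed once Visit 14/Week 52 of Open-label Treatment has been completed". Under 5.5.9, "Subjects who discontinue study treatment should undergo an end of study visit and then be discontinued from the trial". Under 3.1.4, for those who stop early, "The EOT2 visit should be scheduled 28 days (± 7 days) after the last dose of study treatment"; 3.1.2 gives the same interval for the first treatment period. The last scheduled dose is at Week 48.

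**The concern.** The sponsor chose 16 weeks as the period after dosing in which pregnancy should be avoided. Only exclusion 10 carries that figure. The agreement and the fetal-risk information in 10.2 are both tied to the study, which for an individual woman ends well before the 16 weeks are over. The deviation list in SAP Table 5.1 (EXCL10) likewise describes the contraception agreement only in terms of the study period.

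Two things are at stake. If the consent discussion follows 10.2 as written, a woman agrees to a shorter precaution than exclusion 10 sets and is not told that the risk consideration continues. And a pregnancy that begins after the last dose but inside the precaution period need not clearly be reported or followed to outcome, although it is the exposure the precaution was meant to address.

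**Working it through.** The plan derives no figure here, since the 16 weeks is simply stated. The check is calendar arithmetic on the plan's own schedule.

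**Inputs**
- Last dose at Week 48 (Protocol 3.1.4), scheduled Day 337 (SAP Table 1-1).
- End of participation at Week 52 (Protocol 5.5.13), scheduled Day 365 (SAP Table 1-1), window ±7 days (Protocol 6).
- Precaution after the last dose: 16 × 7 = 112 days (exclusion 10).
- End-of-treatment visit for early stoppers: 28 ± 7 days after the last dose (Protocol 3.1.2 to 3.1.4).
- Final safety contact: 30 days after the last visit (Protocol 6).
- SAP on-treatment definition: last dose + 84 days (SAP 2.1.1.4).

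**End of the precaution, completer:** 337 + 112 = Day 449, which is Week 64.

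**Gap in the 10.2 agreement**
- Completer: 449 − 365 = 84 days = 12 weeks.
- Week 52 visit anywhere from Day 358 to Day 372: 449 − 372 = 77 to 449 − 358 = 91 days, or 11 to 13 weeks.
- Week 48 dose also moved within its own ±7-day window (Day 330 to 344): (330 + 112) − 372 = 70 to (344 + 112) − 358 = 98 days, or 10 to 14 weeks.
- Early stopper: 112 − 28 = 84 days; with the ±7 days, 112 − 35 = 77 to 112 − 21 = 91.

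**Gap in 7.3 reporting, completer.** The protocol does not say when a woman ceases to be on study treatment. The nearest text is the Glossary entry for study treatment discontinuation, "Point/time when patient permanently stops taking study treatment for any reason", which points to the last dose.

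| Reading of the end of treatment | Ends on | Left uncovered |
|---|---|---|
| Last dose | Day 337 | 449 − 337 = 112 days (16 weeks) |
| Week 52 visit | Day 365 | 449 − 365 = 84 days (12 weeks) |
| SAP rule, last dose + 84 days | Day 421 | 449 − 421 = 28 days (4 weeks) |

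None of the three readings reaches Day 449.

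**Do other rules close the gap?**
- The final safety contact falls on 365 + 30 = Day 395. That is 449 − 395 = 54 days before the precaution ends, or 47 to 61 days if the Week 52 visit moves within its window.
- SAE reporting (Protocol 7.2.2) runs to 30 days after the last visit, and later only where the investigator suspects a causal link. Pregnancy itself is not among the SAE criteria in 7.2.1, so a post-dose pregnancy without such an event is not captured.
- The last scheduled urine pregnancy test is at Week 52 (Protocol Table 6-1).

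**The case against.** The best defence is that the operative rule is already right. Exclusion 10 is a binding entry criterion, and 10.2 refers to the contraception requirement without setting a rival one, so it can be read as importing the 16 weeks. That is a fair account of the intent, and it is why this is a mismatch of scope. But the same clause in 10.2 then limits the requirement to the study's duration, and a safety instruction should not have two readings.

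Second, women sign the consent form and not section 10.2. The form is a separate document, was not available, and may state 16 weeks. This stands: the harm to consent is conditional, and only the protocol wording is established.

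Third, 5.5.13 distinguishes an individual's participation from the study as a whole, which ends at database lock. If 10.2 means the latter, the gap differs from woman to woman and cannot be computed; for early enrollees it could be small or nil. This also stands as a limit on the 12-week figure, though an agreement whose end depends on database lock would not be a usable instruction.

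Fourth, nothing in the documents requires the reporting window to equal the contraception window, and the 4-week figure borrows an SAP definition that concerns assessments. Both statements are true. Congenital anomalies and SAEs suspected to be causally related remain reportable, which narrows the gap. A post-dose pregnancy with no such event is still left out, and that is a case where outcome follow-up would be informative.

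**Conclusion.** The concern holds. Read literally, 10.2 leaves 12 weeks of the 16-week precaution without an agreement (11 to 13 weeks when the Week 52 visit moves within its window, 10 to 14 when the Week 48 dose moves as well), for completers on schedule and early stoppers alike. Section 7.3 leaves 4 to 16 weeks outside mandatory pregnancy reporting, and 16 is the most literal reading.

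The 10.2 figure assumes that the study means the woman's own participation. The consequence for consent assumes that the form follows 10.2. The number of women of child-bearing potential is not given, so the expected number of affected pregnancies cannot be estimated. Sample size, power, type I error and the primary analysis are untouched. This is a participant-safety point that should be corrected; it does not threaten the trial's conclusions.

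**What to change.** - **Protocol 10.2:** state that the woman agrees to contraception during dosing and for 16 weeks after the last dose, and give the fetal-risk information the same time span. Check that the separate consent form says the same.
- **Protocol 7.3:** require reporting and outcome follow-up of any pregnancy from the first dose through 16 weeks after the last dose, and have women told to inform the site of a pregnancy in that period.
- **Separate minor point:** Protocol 5.5.5 permits no interruption of study treatment, while 6.5.5 requires one after a positive urine pregnancy test. An exception in 5.5.5 referring to 6.5.5 would reconcile them.

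The cost is a wording amendment to these sections, a change to the consent form if it differs, and slightly longer pregnancy reporting. No visits are added. Because there is no scheduled contact after Day 395, reporting in the last part of the window would depend on the woman informing the site.

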10.3 Responsibilities of the investigator and IRB/IEC

Before initiating a trial, the Investigator/institution should obtain approval/favorable opinion from the Institutional Review Board/Independent Ethics Committee (IRB/IEC) for the trial protocol, written informed consent form, consent form updates, subject recruitment procedures (e.g., advertisements) and any other written information to be provided to subjects. Prior to study start, the Investigator is required to sign a protocol signature page confirming his/her agreement to conduct the study in accordance with these documents and all of the instructions and procedures found in this protocol and to give access to all relevant data and records to Novartis monitors, auditors, Novartis Quality Assurance representatives, designated agents of Novartis, IRBs/IECs, and regulatory authorities as required. If an inspection of the clinical site is requested by a regulatory authority, the Investigator must inform Novartis immediately that this request has been made.

10.4 Publication of study protocol and results

Novartis assures that the key design elements of this protocol will be posted in a publicly accessible database such as clinicaltrials.gov. In addition, upon study completion and finalization of the study report the results of this trial will be either submitted for publication and/or posted in a publicly accessible database of clinical trial results.

11 Protocol adherence

This protocol defines the study objectives, the study procedures and the data to be collected on study participants. Additional assessments required to ensure safety of subjects should be administered as deemed necessary on a case by case basis. Under no circumstances should an Investigator collect additional data or conduct any additional procedures for any research related purpose involving any investigational drugs.

Investigators ascertain they will apply due diligence to avoid protocol deviations. If an Investigator feels a protocol deviation would improve the conduct of the study this must be considered a protocol amendment, and unless such an amendment is agreed upon by Novartis and approved by the IRB/IEC and health authorities, where required, it cannot be implemented. All significant protocol deviations will be recorded and reported in the CSR.

13.1 Appendix 1: Clinically notable laboratory values and vital signs

The following criteria will be used to define expanded limits and notable abnormalities of key laboratory tests. Notable values for blood pressure and pulse are presented in [Section 6.5.2](#).

Whether or not any action needs to be taken to address notable laboratory or vital signs values will be determined by the investigator/qualified site staff, taking into account the overall status of the patient. No specific action is pre-defined within this study protocol.

Liver function and related variables

ALT (SGPT)	> 3 x Upper Limit of Normal (ULN)
AST (SGOT)	> 3 x ULN
Total bilirubin	> 1.5 x ULN
Alkaline phosphatase	> 2 x ULN

[figure not shown]
Renal function and electrolyte variables

Creatinine (serum)	> 1.5 x ULN
--------------------	-------------

Hematology values

Hemoglobin	≥ 2.0 g/dL decrease from baseline
Platelet count	< Lower Limit of Normal (LLN)
White blood cell	< 0.8 x LLN
Neutrophils	< 0.9 x LLN
Eosinophils	> 1.1 x ULN
Lymphocytes:	> 1.1 x ULN

